4.2. Selection of the Study Population

4.2.1 Inclusion criteria:

- Adult subjects over 18 years of age.
- SARS CoV2 / COVID 19 disease confirmed by antigen detection tests authorized by INVIMA or by RT-PCR in any of the laboratories that report to the Departmental Health Secretary, approved for the diagnosis of COVID-19 by the National Institute of Health.
- Onset of SARS CoV2 / COVID 19 illness 7 days ago or less.
- Subjects with mild disease.
- Informed consent signature.

4.2.2 Exclusion criteria:

- Medical history of liver disease.
- History of allergy to ivermectin or any of its components.
- Belonging to another clinical trial that evaluates the efficacy of an investigational drug against COVID-19. The use of other treatments outside of clinical trials is allowed.
- Severe pneumonia at the time of randomization.
- Pregnant or nursing women.
- Subjects receiving Warfarin, erdafitinib, or quinidine.
- Subjects who have received the D11AX22 molecule (ivermectin) within 5 days prior to randomization.
- Inability to evaluate recent liver enzymes, no more than 3 days prior to selection.
- Elevation in basal liver enzymes > 1.5 times the normal level.
- Subject whose contact with study personnel occurs between days 5-7 and at that time manifests significant and progressive improvement \geq 48 hours in signs and symptoms of COVID-19.

4.2.3 **Early withdrawal from the study:**

Subjects will be withdrawn from the study:

1. In the event that the investigation product is discontinued within 24 hours of randomization.

4.2.4 Randomization:

Central 1: 1 randomization in blocks of 4 will be generated by a list of random numbers, a separate staff of the telephone allocation system will assign treatment to each of the research participants on a first-come, first-served basis.

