4.3.3 Table of visits and follow-ups

| Visit number (V) | Screening | Randomization | Phone call 1 | Phone call 1 | Phone call 1 | Phone call 1 | Phone call 1 | Phone call 1 | Phone call 1 | Phone call 1 |
|---|------------|---------------|-----------------|-----------------|-----------------|-----------------|-----------------|-----------------|-----------------|-----------------|
| Study deadlines | SCR | D1 | D2 | D3 | D4 | D5 | D8 | D11 | D 15 | D 21 |
| Intervals (days) | | | | | | | ±1 | ±1 | ±1 | ±1 |
| Signed informed consent form | X | | | | | | | | | |
| Inclusion/exclusion criteria | X | X | | | | | | | | |
| Assignment of the research participant number | X | | | | | | | | | |
| Demographic Data | X | | | | | | | | | |
| Medical background check | | X | | | | | | | | |
| Weight | X | | | | | | | | | |
| Vital signs and pulse oximetry | | X | | | | | | | | |
| Calculation of NEWS -2 score: | | X | | | | | | | | |
| Collection of clinical data | | X | | | | | | | | |
| Urine sample to evaluate pregnancy | X | | | | | | | | | |

| | | | | | | | | | | |
|---|-----------------------|----------|----------|----------|----------|----------|----------|----------|----------|----------|
| Blood Sample to evaluate Hepatic enzymes ² | X ² | | | | | | | | | |
| Randomization | | X | | | | | | | | |
| Dispensing and initiating medication/placebo | | X | | | | | | | | |
| Evaluation of the 7-point ordinal scale | | X | X | X | X | X | X | X | X | X |
| Assessment of secondary outcomes - Pt. at home or hospitalized? - Has required oxygen? - Has required ICU? - Vital status - Persists with fever? | | X | X | | | X | X | X | X | X |
| Collection of Serious Adverse Events (SAE) | | | X | | | X | X | X | X | X |
| Pharmacotherapeutic Adherence | | X | | | | X | | | | |
| Remember the need to take the investigation product | | | X | X | X | X | | | | |
| Collect symptoms reported to the admin of the investigation product | | | X | X | X | X | X | X | X | X |
| Record of completion | | | | | | | | | | X |

¹ In the case of hospitalized research participants, the study staff will personally visit the subject and/or contact the physician in charge by telephone, and/or through the medical history will obtain the necessary information and thus be able to determine primary or secondary outcomes

² It will not be necessary to collect the liver enzyme sample if there is a recent result no more than 3 days prior to selection.

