4.5 Data analysis

An interim analysis will be conducted without breaking the blind when 200 research participants have been randomized. The study will be discontinued if this analysis detects a significant treatment effect on the main objective, if it is detected that a significantly larger group of subjects withdraw from the intervention arm due to adverse events, or if no difference is detected between the two groups. Recruitment will continue while this analysis is performed.

The information will be analyzed with Stata version 14 (SE; Stata corporation, College Station, Texas). For this purpose, subjects will be grouped into 2 groups that comprise

- Group 1:** Subjects who received ivermectin
- Group 2:** Subjects who received placebo.

The baseline characteristics of the subjects will be described by descriptive analysis.

The main analysis will be by intent-to-treat. The time until the disappearance of symptoms will be determined when all research subjects reach day 21. Clinical deterioration or death before the 21st will be right censored- on the 21st. Deaths will be included unless there is strong evidence that the cause of death was not associated with COVID-19. The time until the disappearance of symptoms will be presented in a Kaplan-Meier curve and will be compared with the log-rank test. Hazard Ratios will be calculated with their 95% confidence interval through a Cox proportional-hazards model.

¹ 76 subjects included in the study had errors in the enlistment of the investigation product consecutively for three weeks, and will be excluded from the primary analysis.

Secondary outcomes and adverse events in each of the groups will be expressed by absolute and relative frequencies with their corresponding 95% confidence interval. For the univariate analysis in the quantitative variables, statistical parameters of central tendency and dispersion (means and standard deviations) will be described if the variable has a normal distribution. In case of not having a normal distribution, medians and interquartile ranges will be described. The qualitative variables will be measured and analyzed through proportions with their corresponding 95% confidence interval.

To determine the efficacy of the intervention in secondary outcomes, a bivariate analysis will be performed, evaluating the association of treatment, demographic and clinical variables with the different outcomes.

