| Final Amendment 3 to the Study Protocol_September 16, 2020 | 
a. This specific objective was included: "To compare the time between randomization and disappearance of symptoms in subjects receiving the D11AX22 molecule (ivermectin) vs. Placebo"
 
b. The original primary outcome was changed to: "To determine the time until the resolution of the symptoms in the two study groups."
 
c. The original primary outcome becomes a secondary outcome
 | 
Less than 3% of the subjects included to date have had the primary outcome described in Amendment 2 ("To determine the time to deterioration in two or more points of the 7-point ordinal scale in the two study groups."). If this primary outcome were retained, the sample size to obtain adequate statistical power would be unattainable (more than 2000 subjects).
 
With this amendment we intend to meet the general and specific objectives with the initially proposed sample size.
 | No new ICF issued | Approved by INVIMA on November 06, 2020 |
| Final Amendment 4 to the Study Protocol_October 27, 2020 | 
a. Sample size increased to 476
 | 
After the start of the study, 38 subjects who were randomized to receive placebo were given ivermectin by mistake in the enrollment of the investigation product. This occurred consecutively over a period of three weeks, so during this period a total of 76 subjects received ivermectin and none received a placebo.
 
This situation was discussed with the independent data monitoring board. Taking into account that this is a systematic error, in which none of these participants received the randomly assigned investigation product, the exclusion of these 76 subjects from the primary analysis was decided. To preserve the planned sample of 400 subjects and thus preserve the statistical power of the study, an additional 76 participants will be included for a total of 476 participants. The 76 participants excluded from the primary analysis will complete the follow-up established by the protocol.
 | INFORMED CONSENT FORM AND GENERAL INFORMED CONSENT OF THE STUDY_Version 6.0_476 October 27, 2020 | Approved by INVIMA on November 9, 2020: |

Statistical Analysis Plan

(SAP)

| | |
|------------------------|---|
| Protocol Title | Double blind, randomized, controlled clinical trial to investigate the effectiveness of the d11ax22 molecule in adult subjects from Valle del Cauca with initial stages of infection by SARS-CoV-2/ Covid-19. |
| Acronym | EPIC |

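### The only safety ground for stopping counts withdrawals for adverse events at one look; deaths, and serious adverse events that do not end in withdrawal, are part of no stated safety ground

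*Supplement*

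**What the plan says.** Section 4.5 of the latest protocol schedules a single look: "An interim analysis will be conducted without breaking the blind when 200 research participants have been randomized". It lists three grounds for discontinuing the study:

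- efficacy: "The study will be discontinued if this analysis detects a significant treatment effect on the main objective";
- safety: "if it is detected that a significantly larger group of subjects withdraw from the intervention arm due to adverse events";
- no difference: "or if no difference is detected between the two groups".

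It adds: "Recruitment will continue while this analysis is performed". No test or boundary is given for any ground.

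Other sections bear on the safety ground:

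- Protocol 4.1.4 gives product once a day for 5 days; 4.3.5 ends outcome evaluation on day 21.
- The visit table in 4.3.3 collects SAEs on D2, D5, D8, D11, D15 and D21, and vital status on those days and on D1.
- Protocol 4.2.3 removes a subject from the study "In the event that the investigation product is discontinued within 24 hours of randomization". Separately, 4.1.5.2 lists as an outcome the proportion who had to discontinue medication because of adverse events, with no time limit.
- Protocol 4.1.5.1 makes time to symptom resolution the primary outcome. Death and time to deterioration appear among the secondary outcomes.
- The September 2020 SAP has no interim analysis section, and its section 6.4 treats safety as exploratory and descriptive.
- The Summary of Changes, under Amendment 4, says of the dispensing error: "This situation was discussed with the independent data monitoring board". The board is not mentioned in the body of the protocol or in the SAP.

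**The concern.** A safety stopping ground should respond to the harms that matter most. This one responds to a behaviour, withdrawal because of an adverse event, that is largely confined to the days when there is product to stop. A participant who finishes the 5 days and is ventilated or dies on day 12 has a recorded SAE or death but has not withdrawn in any ordinary sense. If the rule is followed as written, an imbalance in such events at the look gives no safety reason to stop, recruitment goes on meanwhile, and no later look is planned.

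**Working it through.** **1. Which harms can reach the safety ground.**

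| Event | Collected? | Counts as a withdrawal for an adverse event? |
|---|---|---|
| Adverse event, serious or not, that makes the participant stop product in days 1–5 | Yes | Yes, if withdrawal means stopping product; unclear if it means leaving the study |
| SAE in days 1–5, dosing completed | Yes | No |
| SAE after the last dose | Yes, to D21 | Not through stopping product, as none is left; only if the participant leaves follow-up because of it |
| Death | Yes, as vital status | Not named; only if the fatal event was first recorded as a withdrawal |

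The second column shows that nothing new need be collected. The third shows that most serious harm falls outside the ground, and that the first row depends on a term that 4.5 does not define.

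**2. Where the look falls.** The plan gives no figure for the safety ground, so there is none to reproduce. The look is at 200 / 476 = 42% of planned randomisations (200 / 400 = 50% of the number intended for the primary analysis). After it, 476 − 200 = 276 participants (58%) are randomised with no further planned look.

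**3. Size of an imbalance that the ground would not register.** Assumptions: 200 randomised 1:1, so 100 per arm, and a two-sided Fisher exact test at 0.05. With k events on ivermectin and none on placebo, p = 2 × C(100,k) / C(200,k).

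- k = 5: 2 × 75,287,520 / 2,535,650,040 = 0.059.
- k = 6: 2 × 1,192,052,400 / 82,408,626,300 = 0.029.

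Other smallest significant splits are 8 vs 1 (p = 0.035), 10 vs 2 (p = 0.033) and 11 vs 3 (p = 0.049). If these were deaths after dosing, none would meet the written safety ground.

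The figure of 100 per arm is not critical. Amendment 4 excludes 76 misdispensed participants from the primary analysis, 38 of them assigned to placebo and so 38 to ivermectin. The documents do not say how many were among the first 200. If all were and were left out, 100 − 38 = 62 per arm remain, and 6 vs 0 gives 2 × C(62,6) / C(124,6) = 2 × 61,474,519 / 4,465,475,476 = 0.028.

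**4. How far the efficacy ground covers the gap.** It states no direction, so harm on the primary outcome could trigger it. Protocol 4.5 censors deaths and deterioration at day 21, which leaves those participants in the risk set as not recovered. SAP 6.1 also allows censoring at death, and SAP 6.5 at the last observation; under either of these a death simply leaves the risk set.

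Take the protocol's treatment, which is the more favourable. Assume 75% recovery by day 21 (protocol 4.4) in both arms apart from the deaths, and let all six who die be participants who would otherwise have recovered. Ivermectin recovery falls from 75% to 69%. As a rough day-21 comparison:

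- SE = √(0.75 × 0.25/100 + 0.69 × 0.31/100) = √0.004014 = 0.0634;
- z = 0.06 / 0.0634 = 0.95, against 1.96.

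Six deaths against none move the primary outcome, but nowhere near significance.

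**5. Blinding.** The look is to leave the blind unbroken, yet the safety ground names the intervention arm. It cannot be applied without data separated by arm, and 4.5 does not say who sees them.

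**The case against.** The strongest objection is the board. An independent data monitoring board existed and was consulted on a serious problem. Its charter is not among the documents, and review of deaths and SAEs is often placed there. A reader might infer from 4.5 that nobody was watching for serious harm; the documents do not support that. What stands is narrower: the protocol states a decision rule, and neither it nor the SAP gives the board any part in it.

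Four other stronger readings should be resisted.

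- *No excess of SAEs could trigger the rule.* An SAE that leads to withdrawal does count. The gap is deaths, and SAEs that do not end in withdrawal.
- *The ground sees only discontinuations in the first 24 hours.* Protocol 4.2.3 says when staff remove a subject; it does not define withdrawal for 4.5. The outcome in 4.1.5.2 has no such limit, and 5.1 lets participants withdraw at any time. The sound statement is that the term is undefined.
- *Ordinary drop-out could stop the trial as harm.* The ground requires that withdrawals be due to adverse events.
- *The efficacy ground gives no cover.* It gives some, heavily diluted, as step 4 shows. Time to deterioration also remains a specific objective (3.2), and the main objective is not expressly defined as the primary outcome alone. Read literally, the third ground might also end the trial, but for lack of difference and not for harm.

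It is also fair to say that a formal test on deaths or SAEs at this look would be weak. With 100 per arm and the same Fisher test, power is 19% for 1% vs 5% and 26% for 6.5% vs 13%. These rates are assumptions; only 6.5% appears in the protocol, as the regional fatality rate in section 2. This is a reason to ask for review by a board and not for a significance threshold. It does not justify leaving these events out.

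**Conclusion.** The point holds in this form: 4.5 ties its only safety ground to withdrawals for adverse events at a single look, so deaths, and SAEs that do not end in withdrawal, are collected but enter no stated safety ground. After the 5 dosing days that is nearly all SAEs. A split as marked as 6 vs 0 deaths would meet no written safety ground, and 276 of 476 participants are randomised after the look.

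The gap itself follows from the text and rests on no numerical assumption. The 6 vs 0 figure assumes 100 per arm and a Fisher test. The step 4 figure assumes 75% underlying recovery in both arms and uses a day-21 comparison in place of the log-rank test. The conclusion concerns what is prespecified, not what the board did. It should be corrected, because it is a stated rule aimed at a poor measure of harm and not just a missing detail.

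**What to change.** Reword the safety ground in 4.5 so that:

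- the existing independent data monitoring board reviews deaths, SAEs and discontinuations for adverse events by assigned arm, whether or not the participant withdrew;
- it does so at the 200-patient look and at any ad hoc meeting;
- it may recommend pausing or stopping on any of these, so that withdrawal is no longer the sole safety criterion.

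In the same edit, define withdrawal as used in 4.5, reconcile it with 4.2.3 and 4.1.5.2, and state who prepares the by-arm table so that the study team stays blinded.

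The cost is protocol wording and one closed table built from data already collected, for a board that already exists. The downside is that a recommendation to stop for harm then rests partly on the board's judgement and not on a single test.

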5. ETHICAL CONSIDERATIONS

5.1. Ethical conduct of the study

The conduct of this study will be in accordance with all local and/or national regulations and directives.

In accordance with international guidelines, this study is considered to comply with the following principles to protect research subjects:

1. **Social and clinical value:** SARS CoV2 is so far a virus with high rates of morbidity and mortality, but without specific treatment. Demonstrating the effectiveness of a safe treatment in the early stages could mitigate the negative impact that this pathology currently has.
2. **Scientific validity:** There is no therapy so far that has been proven to be effective for this pathology in its initial stages. Ivermectin has biological plausibility and an observational study in patients with SARS-CoV-2 suggests clinical utility.
3. **Fair selection of research subjects:** Individuals with a confirmed diagnosis of SARS CoV 2 are chosen. Randomization will guarantee a homogeneous distribution of confounders in both arms.
4. **Risk-benefit ratio - favorable:** Ivermectin is a safe drug, widely used in humans with different pathologies, so we do not anticipate adverse events. The potential benefit to subjects receiving the drug may be greater in mitigating SARS-CoV-2 disease. All subjects will be contributing to the development of science at this time of global emergency, by providing information aimed at improving the management of this disease.
5. **Informed consent:** All subjects must accept their participation in the study by signing an informed consent form and can withdraw their participation at any time.

6. Participation in the study does not generate any economic benefit for the subject, no incentives will be given and since there is no mobilization, transportation and food expenses are not covered.

5.2. Source data and documents

The "source data" is the data contained in the source documents. Source documents are original documents or certified copies and include, but are not limited to, memory aids, medical and hospital records, pre-selection records, informed consent/assent forms, telephone contact records, and worksheets. The purpose of the study source documents is to document the existence of the subjects, and to support the integrity of the data collected in the study. Investigators should maintain the source documents of the study so that they are accurate and legible, and are complete and up-to-date.

The investigator and center staff handling source documents must follow good documentation practices.

5.3. Confidentiality of data and access to participant records

In the event that a subject's medical history is not at the research center, it is the responsibility of the investigator to obtain said history if necessary.

All personal data collected related to subjects, investigators or anyone involved in the study, which may be included in the sponsor's database, will be treated in accordance with all applicable laws and regulations. The data collected should be adequate, relevant and not excessive in relation to the purposes for which it is collected. Each category of data must be adequately justified and be in line with the objective of the study.

Subjects will be assigned a unique identifier by the investigator. Any subject record or data set that is transferred will contain only the identifier; the names of the subject or any information that could make the subject identifiable will not be transferred.

The subjects must be informed that their personal data related to the study will be used by the investigator, in accordance with local data protection laws. The level of disclosure should also be explained to the subject.

The subject must be informed that their medical history may be examined by Quality Management auditors or other authorized persons designated by the investigator, by members of CEI, and by inspectors from regulatory authorities.

When filing or processing personal data relevant to the investigator and/or subjects, all appropriate measures will be taken to safeguard and prevent access to this data by an unauthorized third party.

5.4. Audits and inspections

The Quality Management area or an independent auditor can carry out a quality assurance audit at any time, to verify that the study has been carried out following the protocol and other applicable regulations. Regulatory authorities may conduct an inspection. The investigator must allow direct access to study documents during these inspections and audits.

5.5. Archive

The investigator must keep all study documents after its completion or interruption, for as long as the applicable laws and regulations require. The study documents will be kept for at least 25 years. Study personnel must not destroy or allow the destruction of any study document without written notice.

Archived data may be kept in electronic records, as long as a backup copy is available, and a hard copy can be obtained upon request. The protocol, documentation, approvals, and all other documents related to the study will be kept by the investigator in the CEIP Archive. All documents and data will be made available to the relevant authorities upon request.

5.6. Financial contract and insurance coverage

All parties involved in the conduct of the study will sign a study agreement, if applicable. CEIP has an insurance policy that covers any liability that may arise from the use of the study protocol.

5.7. Publishing policy

The data obtained from this study are the exclusive property of CEIP. Any publication or presentation related to the study should be sent to CEIP for review before the manuscript is submitted. After publication of study results, any participating center may publish or otherwise use its own data, as long as any publication of study data acknowledges the study group. In addition, CEIP will be offered association with all publications of this nature, with the understanding that CEIP has the right to reject such association.

